#### **4.4 Patients or Partners of Patients of Reproductive Potential**

Pregnancy is an exclusion criterion. Women of childbearing potential must not be considering getting pregnant and must avoid pregnancy during the study and for at least 6 months after the last dose of study drug (oral or IV, whichever is later), or longer if requested by local authorities.

Female patients of childbearing potential must have a negative serum pregnancy test result  $\leq 3$  days prior to administration of the first dose of rucaparib. In addition, a serum pregnancy test must be performed  $\leq 3$  days prior to Day 1 of every cycle during the Treatment Phase and at the time of treatment discontinuation. Pregnancy testing will be conducted locally. Treatment should be discontinued immediately in any woman found to have a positive pregnancy test while taking rucaparib and/or nivolumab.

Female patients are considered to be of childbearing potential unless 1 of the following applies:

- Considered to be permanently sterile. Permanent sterilization includes hysterectomy, bilateral salpingectomy, and/or bilateral oophorectomy; or
- Is postmenopausal, defined as no menses for at least 12 months without an alternative medical cause. A high follicle-stimulating hormone (FSH) level consistently in the postmenopausal range (30 mIU/mL or higher) may be used to confirm a postmenopausal state in women not using hormonal contraception or hormonal replacement therapy; however, in the absence of 12 months of amenorrhea, a single FSH measurement is insufficient to confirm a postmenopausal state.

Female patients of reproductive potential must practice highly effective methods (failure rate  $< 1\%$  per year) of contraception with their partners, if of reproductive potential, during treatment and for 6 months following the last dose of rucaparib and/or nivolumab, or longer if requested by local authorities. Highly effective contraception includes:

- Ongoing use of progesterone only injectable or implantable contraceptives;
- Placement of an intrauterine device (IUD) or intrauterine system (IUS);
- Bilateral tubal occlusion;
- Sexual abstinence as defined as complete or true abstinence, acceptable only when it is the usual and preferred lifestyle of the patient; periodic abstinence (eg, calendar, symptothermal, post-ovulation methods) is not acceptable; or

- Male sterilization, with appropriate post vasectomy documentation of absence of sperm in ejaculate.

Patients will be instructed to notify the investigator if pregnancy is discovered either during or within 6 months of completing treatment with study drug.

#### **4.5 Waivers of Inclusion/Exclusion Criteria**

No waivers of these inclusion or exclusion criteria will be granted by the investigator and the sponsor or its designee for any patient enrolling into the study.

## 5 STUDY TREATMENT(S)

### 5.1 Description of Treatment(s) and Storage

Patients will receive open-label oral rucaparib + IV nivolumab combination treatment.

#### 5.1.1 Investigational Drug Product – Rucaparib

Rucaparib camsylate (also known as CO-338; formerly known as PF-01367338 and AG-014447) is an oral formulation. Rucaparib tablets for oral administration will be supplied to the study sites by the sponsor. A brief description of rucaparib is provided in [Table 2](#) with details in the Pharmacy Manual.

**Table 2. Description of Rucaparib Tablets**

Drug Name:	Rucaparib
INN:	Rucaparib
Formulation: (strengths expressed as free base)	Tablet; film coated; 200 mg (blue, round, debossed with C2), 250 mg (white, diamond shape, debossed with C25), 300 mg (yellow, oval, debossed with C3)
How Supplied:	200 mg, 250 mg, and 300 mg (as free base) strength tablets in 60 count bottles. Patients may receive one or more strengths.
Storage Conditions:	15–30°C (59–86°F).

#### 5.1.2 Investigational Drug Product – Nivolumab

Nivolumab, also referred to as BMS-936558-01 or BMS-936558, is a soluble protein consisting of 4 polypeptide chains, which include 2 identical heavy chains and 2 identical light chains (molecular weight: 146 kDa). A brief description of nivolumab is provided in [Table 3](#) with details in the Pharmacy Manual.

**Table 3. Description of Nivolumab for Injection**

BMS Number:	BMS-936558-01
INN	Nivolumab
Other names:	Opdivo, BMS-936558, MDX1106, ONO-4538, anti-PD-1
How Supplied	10 mg/mL concentrate for solution for infusion as 100 mg/10 mL single dose glass vials
Storage Conditions:	As directed on the product label

### 5.2 Packaging and Labeling

#### 5.2.1 Rucaparib Tablets

Rucaparib tablets are provided in 60-count high-density polyethylene (HDPE) bottles with child resistant caps and should be stored in the provided containers and as directed on the product label. Patients will be dispensed one or more strengths depending on their current dose of

rucaparib. The number of bottles of each strength dispensed will be sufficient to supply 28-days treatment per cycle, including a small overage.

Details with respect to packaging and labeling of rucaparib tablets are described in the pharmacy manual.

### 5.2.2 Nivolumab

Nivolumab will be supplied by the sponsor as a 10 mg/mL solution in glass vials.

The vials and outer carton will be labeled according to national regulations for investigational products.

The solution will be diluted for administration as an infusion in sodium chloride 9 mg/mL (0.9%) solution or glucose 50 mg/mL (5%).

Details with respect to packaging and labeling of nivolumab for injection are described in the pharmacy manual.

## 5.3 Method of Assigning Patients to Treatment Groups

All patients enrolled in the study will receive oral rucaparib at an initial dose of 600 mg BID continuously commencing C1D1, and IV nivolumab at an initial dose of 480 mg Q4W commencing C2D1.

## 5.4 Preparation and Administration of Protocol-specified Treatment

The investigator or designee will be responsible for distributing oral study drug to all patients, and the pharmacist or authorized designee will be responsible for preparing the IV study drug for all patients.

Rucaparib and nivolumab will be assigned by an interactive response technology (IRT) system.

### 5.4.1 Rucaparib

Rucaparib 600 mg is administered orally BID (as close as possible to 12 hours apart, preferably at the same times every day) with water starting on Day 1. Study drug (tablets) may be taken with or without food. Tablets should be swallowed whole without crushing or chewing. Oral study drug will be provided as 200 mg, 250 mg, and 300 mg [as free base] dose strength tablets. If a patient vomits after dosing, the dose will not be made up; the patient will take their next dose at the regularly scheduled interval.

Each treatment cycle of oral study drug is 28 days, and treatment will begin on Day 1 of Cycle 1. Patients will be provided a sufficient quantity of study drug to last until Day 1 of the next treatment cycle. Patients will be instructed to bring their study drug tablets and all containers (empty, partially used, and/or unopened) to the next scheduled visit for reconciliation by site personnel.

#### 5.4.2 Nivolumab

Nivolumab is administered as 480 mg via a 30-minute IV infusion on Day 1 of every 28-day cycle, starting on **Cycle 2 Day 1**. IV study drug infusion should be prepared as specified in the Pharmacy Manual. Refer to the current version of the IB and/or Pharmacy Manual for complete storage, handling, dispensing, and infusion information.

### 5.5 Dose Modification Criteria

Doses of oral study drug (rucaparib), and/or IV study drug (nivolumab), may be interrupted or delayed for toxicity and other protocol-specified criteria. Dose reductions are permitted for oral study drug but not for IV study drug (see [Section 5.5.1](#)). The assessment for delay or discontinuation should be made separately for the oral study drug (rucaparib) and the IV study drug (nivolumab); however, if toxicity is considered related to all study drugs or if the investigator is unable to determine which study drug is the cause of the AE, then all study drugs in the combination should be delayed and/or discontinued. Treatment may be prematurely discontinued due to withdrawal of consent, unacceptable toxicity, disease progression, completion of treatment cycles, or termination of the study, whichever occurs first.

Dose modification and re-treatment of oral and/or IV study drug are to be based on the criteria presented in [Table 4](#).

**Table 4. Dose Modification and Re-treatment Criteria for Oral and IV Study Drugs**

Adverse Event	Severity (CTCAE Grade)	Oral Study Drug (rucaparib)		IV Study Drug (nivolumab)	
		Dose Modification 	Re-treatment	Dose Modification 	Re-treatment
Non-hematological Non-skin AEs					
Adverse event, except fatigue	2	None	N/A	Hold	Grade ≤ 1 or baseline 
Any adverse event (related events lasting > 7 days for nivolumab, exceptions below)	3 or 4	Hold	≤ Grade 2 	Discontinue	
Exceptions with rucaparib					
Alopecia, nausea, vomiting, or diarrhea adequately controlled with systemic antiemetic/antidiarrheal medication administered in standard doses according to the study center routines	3 or 4	None			
ALT/AST provided no signs of liver dysfunction (see laboratory section below)	3	None			
Exceptions with nivolumab					
Uveitis, pneumonitis, bronchospasm, neurological toxicity, myocarditis, hypersensitivity reaction or infusion reaction of any duration	3			Discontinue	
Endocrinopathies, adequately controlled with only physiologic hormone replacement	3			Hold	Grade ≤ 1 or baseline 
Drug-related adrenal insufficiency or hypophysitis	2			Hold	Grade ≤ 1 or baseline 
Adrenal insufficiency regardless of control with hormone replacement	3			Discontinue	
Laboratory abnormalities except as specified below	3			Hold	Grade ≤ 1 or baseline 
Drug-related ALT, AST, or bilirubin	3			Discontinue 	
Adverse event or laboratory abnormality except for those below that do not require delay	4			Discontinue	
Asymptomatic amylase or lipase	4			Hold	Grade ≤ 1 or baseline 

**Table 4. Dose Modification and Re-treatment Criteria for Oral and IV Study Drugs**

Adverse Event	Severity (CTCAE Grade)	Oral Study Drug (rucaparib)		IV Study Drug (nivolumab)	
		Dose Modification 	Re-treatment	Dose Modification 	Re-treatment
Isolated electrolyte imbalances/abnormalities not associated with clinical sequelae/corrected w/supplementation /appropriate management w/in 72 hours of onset	4			Hold	Grade ≤ 1 or baseline 
Endocrinopathy AEs 	3			Hold	Grade ≤ 1 or baseline 
Non-hematological Toxicity (Skin)					
Adverse event	3	Hold	Grade 2 	Hold	
Hematological Toxicity					
Hematological toxicity (related events lasting >7 days for nivolumab, exceptions below)	3-4	Hold 	Grade 2 	Discontinue	
Confirmed MDS or AML (all new secondary malignancies are Grade 4 per CTCAE 5.0)	4	Discontinue		Discontinue	
Exceptions with nivolumab					
Laboratory abnormalities except as specified below	3			Hold	Grade ≤ 1 or baseline 
Thrombocytopenia > 7 days or associated with bleeding	3			Discontinue	
Laboratory abnormality except for those below that do not require delay	4			Discontinue	
Neutropenia ≤ 7 days	4			Hold	Grade ≤ 1 or baseline 
Lymphopenia or leukopenia	4			Hold	Grade ≤ 1 or baseline 
Laboratory Abnormalities					
Laboratory abnormality	3	Hold	Grade 2 	Hold	
ALT, AST, and/or bilirubin abnormalities	2	None	N/A	Hold 	Grade ≤ 1 or baseline 
ALT/AST elevations	3	None, provided no	N/A	Discontinue 	

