**Table 4. Dose Modification and Re-treatment Criteria for Oral and IV Study Drugs**

Adverse Event	Severity (CTCAE Grade)	Oral Study Drug (rucaparib)		IV Study Drug (nivolumab)	
		Dose Modification 	Re- treatment	Dose Modification 	Re- treatment

 
Prior to re-initiating treatment in a patient with a dosing delay > 14 days, the study medical monitor/designee must be consulted.
 
					

Abbreviations: AE = adverse event; ALT = alanine aminotransferase; AML = acute myeloid leukemia; AST = aspartate aminotransferase; BID = twice daily; CTCAE = Common Terminology Criteria for Adverse Events; DILI = drug-induced liver injury; IV = intravenous; MDS = myelodysplastic syndrome; N/A = not applicable; ULN = upper limit of normal

Oral drug may be discontinued for any AE, laboratory abnormality, or intercurrent illness which, in the judgment of the investigator, presents a substantial clinical risk to the patient with continued oral study treatment dosing. In addition, and at the discretion of the investigator, the dose of oral study drug may be held and/or reduced for Grade 2 toxicity not adequately controlled by concomitant medications and/or supportive care.

In addition to the criteria below, nivolumab should be held if there is any AE, laboratory abnormality, or intercurrent illness that, in the judgment of the investigator, warrants delaying the dose of study medication or discontinued if there is any AE, laboratory abnormality, or intercurrent illness that, in the judgment of the investigator, presents a substantial risk to the patient with continued IV study drug dosing. Patients who require dose hold should be re-evaluated weekly or more frequently if clinically indicated and resume dosing during the next scheduled dosing window (Cycle X, Day 1 ±3 days) after re-treatment criteria are met.

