## Skin Adverse Event Management Algorithm

Rule out non-inflammatory causes. If non-inflammatory cause, treat accordingly and continue I-O therapy.

Patients on IV steroids may be switched to an equivalent dose of oral corticosteroids (e.g. prednisone) at start of tapering or earlier, once sustained clinical improvement is observed. Lower bioavailability of oral corticosteroids should be taken into account when switching to the equivalent dose of oral corticosteroids.

[figure not shown]
\*Refer to NCI CTCAE v4 for term-specific grading criteria.

^If SJS/TEN is suspected, withhold I-O therapy and refer patient for specialized care for assessment and treatment. If SJS or TEN is diagnosed, permanently discontinue I-O therapy.

27-Jun-2019

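### Table 4 has a single skin rule (Grade 3, hold both drugs) and none for Grade 4, while Appendix 6 requires nivolumab to be stopped for good once SJS or TEN is diagnosed; the two places need reconciling

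*Combined protocol and SAP*

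**What the plan says.** Section 5.5 states: "Dose modification and re-treatment of oral and/or IV study drug are to be based on the criteria presented in" Table 4. Three features of that table matter here.

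- The first block is headed "Non-hematological Non-skin AEs". It contains the general Grade 3 or 4 row, "Any adverse event (related events lasting > 7 days for nivolumab, exceptions below" (closing bracket omitted). It also contains, under the nivolumab exceptions, the Grade 4 row "Adverse event or laboratory abnormality except for those below that do not require delay", whose action is Discontinue.
- The skin block, headed "Non-hematological Toxicity (Skin", has one row, which reads in the extracted text as "Adverse event 3 Hold Grade 2 4 Hold". That is Grade 3: hold rucaparib and re-treat at Grade 2 subject to footnote 4, and hold nivolumab. The nivolumab re-treatment cell is empty in the text available.
- Under footnote 2, patients held on nivolumab are to "resume dosing during the next scheduled dosing window" once re-treatment criteria are met. Under footnote 4, rucaparib may continue at the same or a lower dose at the investigator's discretion.

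The Appendix 6 skin algorithm says that I-O therapy is withheld and the patient referred if SJS or TEN is suspected, and then: "If SJS or TEN is diagnosed, permanently discontinue I-O therapy". Section 5.6 identifies nivolumab as the I-O agent in this protocol. Appendix 6 describes itself as guidance.

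**The concern.** A site following Table 4 alone finds an instruction for the milder of the two severe skin grades and none for the worse one. For a diagnosed case of SJS or TEN graded 3, it finds a hold that can end in re-treatment, whereas Appendix 6 calls for a permanent nivolumab stop. Nothing in the skin row sends the reader to Appendix 6.

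Two things are at stake. The first is patient safety, because the unclear cases are the most severe skin reactions. The second is consistent safety reporting. Section 9.8.1 tabulates adverse events leading to interruption or delay separately from those leading to discontinuation, so two sites with the same reaction could place it in different tables. The response-rate endpoint and the two-stage decision rule are not shown to be affected.

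**Working it through.** No sample size, error rate or event count is involved, so the check sets the passages side by side.

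**Step 1: count the skin instructions.** In Table 4 and its footnotes there is 1 skin row (Grade 3), 0 Grade 4 skin rows and 0 mentions of SJS or TEN.

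**Step 2: ask whether a general Grade 4 row reaches skin events.** Both candidate rows in the non-hematological part stand under the non-skin heading. The hematological block repeats its own Grade 3-4 row and its own Grade 4 nivolumab discontinuation row. The table is therefore built block by block and does not rely on the first block carrying over.

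**Step 3: lay out the cases.**

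| Case | Table 4, rucaparib | Table 4, nivolumab | Appendix 6 skin text |
|---|---|---|---|
| Grade 3 skin event | Hold; re-treat at Grade 2, footnote 4 | Hold; re-treatment cell empty as extracted | Figure not available |
| Grade 4 skin event | No skin row | No skin row | Figure not available |
| SJS/TEN suspected | Not named; follows the grade | Not named; follows the grade | Withhold nivolumab, refer |
| SJS/TEN diagnosed, graded 3 | Hold, resumable | Hold | Permanent nivolumab stop; rucaparib not named |
| SJS/TEN diagnosed, graded 4 | No skin row | No skin row | Permanent nivolumab stop; rucaparib not named |

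The direct conflict is the nivolumab entry in the fourth line. The second and fifth lines show the missing rule. No passage deals specifically with rucaparib after SJS or TEN.

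**Step 4: look for a link between the two places.** Hepatic footnotes 5 and 8 send the reader to the hepatic algorithm in Appendix 6. The skin row has no such pointer. Section 3.2 refers to Section 5.5.1.2 for study-specific withdrawal rules, but that section says only that IV dose reductions are not permitted.

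**Step 5: read footnote 3.** It lets nivolumab resume at Grade 2 skin toxicity only where there has been no drug-related Grade 3 skin event. This bears on resumption after a Grade 3 event. It does not address Grade 4, SJS or TEN, and no footnote 3 marker appears on the skin row as extracted.

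**Step 6: a secondary point of the same kind.** In the non-skin block, a Grade 2 event other than fatigue holds nivolumab. The general Grade 3 row reaches nivolumab only for related events lasting more than 7 days. A related Grade 3 event that is not among the listed exceptions has no specified nivolumab row in its first 7 days.

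**The case against.** The strongest case against is that the protocol already provides for these patients.

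- **Stopping rules elsewhere.** Footnote 1 permits stopping rucaparib on investigator judgment. Footnote 2 says nivolumab should be held or discontinued on the same basis. Section 3.2 makes discontinuation mandatory once the investigator judges the safety risk unacceptable. Section 5.5 calls for delaying or discontinuing all study drugs when toxicity is attributed to all of them or attribution is unclear. The dosing-delay rows also limit a hold, to 8 weeks from the previous dose for nivolumab and 14 consecutive days for rucaparib, with exceptions. All of this stands. A reader might infer that a Grade 4 skin event has no instruction at all; the documents do not support that. What is missing is a specified rule for the grade.
- **The non-skin heading is not strictly kept.** The block lists alopecia, which exclusion criterion 4 treats as a skin disorder, and it mixes in laboratory rows. A reader could take the nivolumab Grade 4 row as general. That is a fair reading, but it goes against the heading and against the block-by-block structure in Step 2, and it would not supply a rucaparib rule.
- **Grade rule and diagnosis rule can work in sequence.** A hold while SJS or TEN is only suspected agrees with Appendix 6. This narrows the conflict to the diagnosed case, where the table still says hold.
- **Appendix 6 may be fuller than it appears.** The flow chart of the skin algorithm was not available for this review and may carry a Grade 4 instruction. It would still sit in guidance that the skin row does not cite.
- **The secondary point has partial cover.** A Grade 3 event that passed through Grade 2 would already have triggered a hold, and footnote 2 reaches the rest by judgment.

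**Conclusion.** The point holds in limited form. Read as written, the table that governs dose modification gives a hold where Appendix 6 requires a permanent nivolumab stop (SJS or TEN diagnosed and graded 3). It also has a skin rule for Grade 3 but none for Grade 4. This is worth correcting in the next amendment because it bears on patient safety and on how events are classified in the Section 9.8.1 tables.

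The number of patients affected cannot be derived from the documents, which give no rate of severe skin reactions. It is assumed to be small within the planned 28 to 53 patients.

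The conclusion rests on two assumptions: that block headings define the scope of the rows beneath them, and that a diagnosed case may be graded 3, since the documents do not state the grade of SJS or TEN. It does not rest on the empty nivolumab re-treatment cell, which may be an extraction effect. No view is taken on which clinical rule is right.

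**What to change.** Reconcile Table 4's skin rows with the Appendix 6 skin algorithm and with footnote 3. Grade 3 skin events, Grade 4 skin events, suspected SJS/TEN and diagnosed SJS/TEN should each carry one instruction and one re-treatment condition per drug, the same in both places. Add a pointer from the skin rows to the algorithm, as footnotes 5 and 8 do for hepatic events. In the same edit, reconcile the Grade 2 and Grade 3 nivolumab rows of the non-skin block so that related Grade 3 events in their first 7 days have a stated instruction. The clinical content is for the sponsor's medical team.

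The cost is table and footnote wording in the next amendment, with no added procedures or patients.

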**Table 4. Dose Modification and Re-treatment Criteria for Oral and IV Study Drugs**

Adverse Event	Severity (CTCAE Grade)	Oral Study Drug (rucaparib)		IV Study Drug (nivolumab)	
		Dose Modification 	Re-treatment	Dose Modification 	Re-treatment
		signs of liver dysfunction 			
ALT/AST elevations	4	Hold	≤Grade 2 Reduce dose 	Discontinue	
ALT or AST > 3 × ULN AND bilirubin > 2 × ULN (suspected DILI)		Hold  Follow guidelines in Section 8.10		Discontinue	
Creatinine elevations	2 (≥ 1.5 x baseline  )	None	N/A	Hold	Grade ≤ 1 or baseline 
Creatinine elevations	3	Hold	Grade 2 	Hold	Grade ≤ 1 or baseline 
Exception with nivolumab					
Grade 3 lymphopenia or asymptomatic amylase or lipase	3			None	
Dosing-related					
Any event that leads to delay in dosing lasting > 8 weeks from the previous dose requires discontinuation, with the exception of dosing delays to allow for prolonged steroid tapers to manage AEs. 
 
Dosing delays lasting > 8 weeks from the previous dose that occur for non-drug-related reasons may be allowed if approved by the study medical monitor/designee
 
				Discontinue	
Toxicity despite dose reduction steps to 200 mg BID or interruption of oral drug for > 14 consecutive days except if allowed if approved by the study medical monitor/designee.		Discontinue			

**Table 4. Dose Modification and Re-treatment Criteria for Oral and IV Study Drugs**

Adverse Event	Severity (CTCAE Grade)	Oral Study Drug (rucaparib)		IV Study Drug (nivolumab)	
		Dose Modification 	Re- treatment	Dose Modification 	Re- treatment

 
Prior to re-initiating treatment in a patient with a dosing delay > 14 days, the study medical monitor/designee must be consulted.
 
					

Abbreviations: AE = adverse event; ALT = alanine aminotransferase; AML = acute myeloid leukemia; AST = aspartate aminotransferase; BID = twice daily; CTCAE = Common Terminology Criteria for Adverse Events; DILI = drug-induced liver injury; IV = intravenous; MDS = myelodysplastic syndrome; N/A = not applicable; ULN = upper limit of normal

Oral drug may be discontinued for any AE, laboratory abnormality, or intercurrent illness which, in the judgment of the investigator, presents a substantial clinical risk to the patient with continued oral study treatment dosing. In addition, and at the discretion of the investigator, the dose of oral study drug may be held and/or reduced for Grade 2 toxicity not adequately controlled by concomitant medications and/or supportive care.

In addition to the criteria below, nivolumab should be held if there is any AE, laboratory abnormality, or intercurrent illness that, in the judgment of the investigator, warrants delaying the dose of study medication or discontinued if there is any AE, laboratory abnormality, or intercurrent illness that, in the judgment of the investigator, presents a substantial risk to the patient with continued IV study drug dosing. Patients who require dose hold should be re-evaluated weekly or more frequently if clinically indicated and resume dosing during the next scheduled dosing window (Cycle X, Day 1 ±3 days) after re-treatment criteria are met.

Patients may resume treatment with IV study drug when the drug-related AE(s) improve to Grade ≤ 1 or resolve to baseline value, with the following exceptions which are allowed: Grade 2 fatigue, Grade 2 skin toxicity (if no Grade 3 drug related skin AE). For patients with Grade 2 AST, ALT, or total bilirubin elevations, dosing may resume when laboratory values return to baseline and management with corticosteroids, if needed, is complete. Drug-related pulmonary toxicity, diarrhea or colitis must have resolved to baseline before treatment is resumed. Patients with persistent Grade 1 pneumonitis after completion of a steroid taper over at least 1 month may be eligible for retreatment if discussed with and approved by the study medical monitor. Patients with drug-related endocrinopathies adequately controlled with only physiologic hormone replacement may resume treatment after consultation with the study medical monitor. Adrenal insufficiency requires discontinuation regardless of control with hormone replacement.

The patient may continue at same or reduced dose at the discretion of the investigator. If treatment is resumed at the same dose, and the patient experiences the same toxicity, treatment should be interrupted, then resumed at a reduced dose following improvement of the event to ≤ CTCAE Grade 2. If the patient continues to experience toxicity, additional dose reduction steps are permitted; however, the investigator should consult with the sponsor's medical monitor before reducing to 300 mg BID.

In most cases of Grade 3 ALT or AST elevation, IV study drug will be permanently discontinued. For patients with Grade 3 ALT or AST elevations after the start of IV dosing, but on a background of previous elevations on the first cycle of oral study drug, IV study drug hold is required, but discontinuation is not required, if ALT/AST elevations begin to resolve before the next scheduled infusion, and toxicity is considered to be mainly related to oral study treatment, after the investigator discusses the case with the study medical monitor. Levels will be monitored every 3 days; if they continue to rise more than 20%, the Hepatic

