**Table 4. Dose Modification and Re-treatment Criteria for Oral and IV Study Drugs**

Adverse Event	Severity (CTCAE Grade)	Oral Study Drug (rucaparib)		IV Study Drug (nivolumab)	
		Dose Modification 	Re-treatment	Dose Modification 	Re-treatment

Adverse Event Management Algorithm for a Grade 3 event will be followed (see [Appendix 6](#)). Treatment with IV drug may be resumed if levels return to Grade 2. If total bilirubin elevations > 2 × ULN accompany any of the ALT/AST elevations, IV drug should be discontinued.

Such as, hyper- or hypothyroidism, or glucose intolerance, that resolve or are adequately controlled with physiologic hormone replacement (corticosteroids, thyroid hormones) or glucose-controlling agents, respectively, may not require discontinuation after discussion with and approval from the study medical monitor/designee. Grade 4 drug-related adrenal insufficiency or hypophysitis requires discontinuation regardless of control with hormone replacement.

If any blood parameters remain clinically abnormal > 4 weeks of dose interruption, the patient should be referred to hematologist for further investigations. Bone marrow analysis and/or blood cytogenetic analysis should be considered at this stage according to standard hematological practice.

For patients with Grade 2 ALT or AST elevations with onset after dosing of oral study drug, IV study treatment hold is not required if ALT/AST elevations begin to resolve before the next scheduled infusion and toxicity is considered to be mainly related to oral study treatment. If a subsequent ALT/AST increase of more than 20% is observed following infusion of IV study drug, the next IV study drug administration will be held and, if further increase is observed, the Hepatic Adverse Event Management Algorithm will be followed (see [Appendix 6](#)). In this case, IV study drug should be discontinued if Grade 2 elevations return post re-challenge. If total bilirubin elevations > 2 × ULN accompany any of the ALT/AST elevations, IV drug should be discontinued.

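### Table 4 tells sites both to hold and resume nivolumab, and to stop it for good, for Grade 2 drug-related adrenal insufficiency; the Grade 3 drafting is unclear

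*Combined protocol and SAP*

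**What the plan says.** Section 5.5 makes Table 4 the basis for dose modification and re-treatment with both drugs. For nivolumab, these entries bear on adrenal insufficiency:

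- **Grade 2 row**, "Drug-related adrenal insufficiency or hypophysitis": hold, with re-treatment at Grade 1 or lower, or baseline. The cell carries the marker for footnote 3.
- **Grade 3 adrenal row**, "Adrenal insufficiency regardless of control with hormone replacement": discontinue, with no re-treatment entry.
- **First Grade 3 endocrinopathy row**, "Endocrinopathies, adequately controlled with only physiologic hormone replacement": hold, with re-treatment under footnote 3.
- **Second Grade 3 endocrinopathy row**, "Endocrinopathy AEs", which carries footnote 6: hold, with re-treatment under footnote 3.
- **Footnote 3**, on resuming nivolumab: "Patients with drug-related endocrinopathies adequately controlled with only physiologic hormone replacement may resume treatment after consultation with the study medical monitor". The next sentence is "Adrenal insufficiency requires discontinuation regardless of control with hormone replacement".
- **Footnote 6**: certain endocrinopathies that resolve or are "adequately controlled with physiologic hormone replacement (corticosteroids, thyroid hormones") may not require discontinuation, subject to the medical monitor's approval. It ends: "Grade 4 drug-related adrenal insufficiency or hypophysitis requires discontinuation regardless of control with hormone replacement".

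**The concern.** A site with a Grade 2 event looks up the row, is told to hold, and is sent to footnote 3 for the conditions of restarting. That footnote says the drug must be stopped. One site can follow the row and another the footnote, each within the protocol, and treat the same immune-mediated event in opposite ways. Footnote 2 adds weight to the difference, since a patient on hold is to resume at the next dosing window once the re-treatment criteria are met.

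Reporting is also touched. Section 9.8.1 plans separate tables for treatment-emergent events leading to discontinuation and for those leading to interruption or delay. Which table a Grade 2 adrenal event enters would depend on the sentence the site happened to follow, as well as on the clinical course.

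**Working it through.** The plan gives no figure to reproduce and no arithmetic applies. The check sets the entries side by side by grade, for adrenal insufficiency and nivolumab only.

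| Grade | Adrenal row | General rows | Footnote 3 | Footnote 6 | Result |
|---|---|---|---|---|---|
| 2 | Hold, re-treat under footnote 3 | Hold, re-treat under footnote 3 (Grade 2 adverse events) | Discontinue (no grade stated) | Silent | Direct contradiction |
| 3 | Discontinue | Hold, re-treat (two endocrinopathy rows) | Discontinue | Mandatory stop named only at Grade 4 | Specific entries agree; drafting unclear |
| 4 | None | Discontinue (Grade 4 adverse events) | Discontinue | Discontinue | No conflict |

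**Grade 2.** The row and its own footnote cannot both be followed. Two features of the text make it hard to confine the footnote sentence to Grade 3. First, footnote 3 states a grade where it means one: it does so for fatigue, skin toxicity and liver tests. Second, the Grade 3 adrenal row has no re-treatment entry and no footnote 3 marker, whereas the Grade 2 adrenal row has both. The conflict concerns adrenal insufficiency only. Hypophysitis shares the Grade 2 row but is not named in the footnote 3 sentence.

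**Grade 3.** The row that names adrenal insufficiency says discontinue, and footnote 3 agrees. The uncertainty comes from three things together:

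1. Footnote 6 is attached to a Grade 3 row that says hold, but its adrenal sentence speaks of Grade 4.
2. Footnote 6 lists corticosteroids among the replacement hormones, so a reader may take adrenal insufficiency to fall within its scope.
3. Table 4 does not say that a specific row takes precedence over a general one.

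**Other places that might settle it.**

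- Section 3.2 refers to nivolumab withdrawal rules in Section 5.5.1.2. That section says only that dose reductions are not permitted.
- Footnote 2 lets the investigator hold or discontinue on judgment. It does not lift a discontinuation that another entry makes mandatory.
- The medical-monitor route in footnote 3 comes immediately before the adrenal sentence, which reads as an exception to it.
- The Appendix 6 endocrinopathy algorithm is a figure that is not reproduced in the text available here, so nothing can be said about its content.

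**The case against.** The best defence at Grade 2 is that the last sentence of footnote 3 merely restates the Grade 3 adrenal row. It repeats that row's phrase about hormone replacement and follows the sentence on controlled endocrinopathies, so it could be a carve-out from the Grade 3 endocrinopathy row, leaving the Grade 2 row intact. This may be what was meant. But nothing in the sentence limits it to Grade 3, and the Grade 2 adrenal cell cites the footnote directly. The text needs a grade qualifier or a changed row either way.

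At Grade 3 the defence largely succeeds. A reader might infer that Grade 3 also carries two opposite instructions, or that three thresholds are in force: any grade, Grade 3 and Grade 4. The documents do not support that. The Grade 3 adrenal row reads naturally as an exception to the general endocrinopathy row above it. Footnote 6 requires discontinuation at Grade 4; it does not say that a Grade 3 event may resume, and its examples are thyroid disorders and glucose intolerance. The row that carries footnote 6 also sits directly after two Grade 4 exceptions, which may explain why the footnote speaks of Grade 4. What remains is that a Grade 4 sentence on a Grade 3 hold row is confusing as printed.

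It would likewise go too far to say that sites cannot apply the table. Investigator judgment under footnote 2 and the monitor's role under footnotes 3 and 6 reduce the ambiguity in practice, though they do not remove the Grade 2 contradiction.

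**Conclusion.** The point holds in a limited form. At Grade 2 the row and the footnote it cites give opposite nivolumab instructions for drug-related adrenal insufficiency, and no readable part of the protocol reconciles them. At Grade 3 the specific entries agree and the fault is unclear drafting. Grade 4 is consistent.

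The number of patients affected is unknown because the documents give no frequency for this event. The effect on analysis is confined to nivolumab exposure and to the descriptive discontinuation and interruption/delay tables. The Simon two-stage figures for Cohort A1 do not depend on it. The reason to act is mainly patient safety.

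The conclusion assumes that the rows and footnote markers of Table 4 are as they appear in the text. Confidence is high for Grade 2 and lower for Grade 3, where a reader who lets the specific row govern finds no conflict. The Appendix 6 figure might state a rule by grade; even so, the wording inside Table 4 would still conflict at Grade 2.

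**What to change.** Reconcile the Grade 2 adrenal row with the closing sentence of footnote 3. Then clarify footnote 6 and the two Grade 3 endocrinopathy rows against the Grade 3 adrenal row, checking that the row carrying footnote 6 bears the intended grade. The table should end with one nivolumab instruction for adrenal insufficiency at each grade, or a stated order of precedence between specific and general rows. Check the result against the Appendix 6 endocrinopathy algorithm. Which rule applies at each grade is for the sponsor's clinical team to decide; this review proposes none.

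The cost is table and footnote wording in a protocol amendment. Sample size, endpoints and planned analyses do not change.
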